8.2.2. Adverse Event Summaries

An overall summary of AEs by treatment group will include the following:

- Number (%) of subjects reporting any TEAEs
- Number (%) of subjects reporting any DLTs (would be Phase 1 only)
- Number (%) of subjects reporting any treatment-related TEAEs
- Number (%) of subjects reporting any serious TEAEs
- Number (%) of subjects reporting any Grade 3 or 4 TEAEs
- Number (%) of subjects with INCB039110 dose reductions because of TEAEs
- Number (%) of subjects who temporarily interrupted INCB039110 because of TEAEs
- Number (%) of subjects who permanently discontinued INCB039110 because of TEAEs
- Number (%) of subjects with ibrutinib dose reductions because of TEAEs
- Number (%) of subjects who temporarily interrupted ibrutinib because of TEAEs
- Number (%) of subjects who permanently discontinued ibrutinib because of TEAEs
- Number (%) of subjects with dose reductions of any study drug because of TEAEs
- Number (%) of subjects who temporarily interrupted any study drug because of TEAEs
- Number (%) of subjects who permanently discontinued any study drug because of TEAEs
- Number (%) of subjects who had a fatal TEAE
- Number (%) of subjects reporting any AEs related to reference therapy

The following summaries will be produced by MedDRA term (if ≤ 10 subjects appear in a table, then a listing may be appropriate):

- Number (%) of subjects reporting TEAEs by system organ class and preferred term
- Number (%) of subjects reporting TEAEs by preferred term in decreasing order of frequency
- Number (%) of subjects reporting TEAEs by system organ class, preferred term, and highest CTCAE grade
- Number (%) of subjects reporting any Grade 3 or 4 TEAEs by system organ class and preferred term
- Number (%) of subjects reporting any Grade 3 or 4 TEAEs by preferred term in decreasing order of frequency
- Number (%) of subjects reporting treatment-related TEAEs by system organ class and preferred term
- Number (%) of subjects reporting treatment-related TEAEs by preferred term in decreasing order of frequency
- Number (%) of subjects reporting treatment-related TEAEs by system organ class, preferred term, and highest CTCAE grade
- Number (%) of subjects reporting any Grade 3 or 4 treatment-related TEAEs by system organ class and preferred term
- Number (%) of subjects reporting any Grade 3 or 4 treatment-related TEAEs by preferred term in decreasing order of frequency
- Number (%) of subjects reporting TEAEs leading to death by system organ class and preferred term
- Number (%) of subjects reporting serious TEAEs by system organ class and preferred term
- Number (%) of subjects reporting serious TEAEs by preferred term in decreasing order of frequency
- Number (%) of subjects reporting treatment-related serious TEAEs by system organ class and preferred term
- Number (%) of subjects reporting TEAEs leading to dose reduction by system organ class and preferred term
- Number (%) of subjects reporting TEAEs leading to dose interruption by system organ class and preferred term
- Number (%) of subjects reporting TEAEs leading to discontinuation of medication by system organ class and preferred term
- Number (%) of subjects reporting TEAEs requiring concomitant medications by system organ class and preferred term

8.3. Clinical Laboratory Tests

8.3.1. Laboratory Value Definitions

Laboratory values and change from baseline values will be summarized descriptively by visit. The baseline value will be determined using the last nonmissing values collected before the first dose. For baseline laboratory candidates with the same date and time, additional rules may be provided after consultation with the medical monitor to delineate which value will be defined as baseline.

Laboratory test values outside the normal range will be assessed for severity based on CTCAE grade or similar criteria where clinical intervention is required for CTCAE grading. The incidence of abnormal laboratory values and shift tables relative to baseline will be tabulated.

8.3.2. Laboratory Value Summaries

Clinical laboratory tests, including hematology and serum chemistry (see [Appendix A](#)), will be performed for each subject during the study in accordance with Table 9 of Protocol Amendment 5 (dated 18 JUN 2020).

If specific safety issues arise, then additional unscheduled laboratory tests or analyses may be performed at the discretion of the investigator.

All test results and associated normal ranges from central laboratories will be reported in SI units. All tests with numeric values will have a unique unit per test. Any laboratory test results and associated normal ranges from local laboratories will be converted to SI units. For the limited number of cases where the associated normal ranges from a local laboratory cannot be obtained despite due diligence, a set of standard normal ranges based on documented reference ranges will be applied to facilitate reporting the test results.

When there are multiple nonmissing laboratory values for a subject's particular test within a visit window, the convention shown in [Table 4](#) will be used to determine the record used for by-visit tabulations and summaries.

Table 4: Identification of Records for By-Visit Summaries

Priority	Laboratory Visit	Central or Local Laboratory	Proximity to Visit Window	Tiebreaker
1	Scheduled	Central	In-window	Use smallest laboratory sequence number
2	Scheduled	Local	In-window	
3	Unscheduled	Central	In-window	
4	Unscheduled	Local	In-window	
5	Scheduled	Central	Out-of-window	
6	Scheduled	Local	Out-of-window	

Laboratory parameters will be summarized. Shift tables based on worst postbaseline value recorded will use all postbaseline values. Other laboratory parameters collected will only be listed in an appendix to the CSR in their original units without SI conversions. A detailed listing of the serum chemistry, hematology, and urinalysis tests is provided in [Appendix A](#).

Numeric laboratory values will be summarized descriptively, and non-numeric test values will be tabulated. In addition, line graph and box-and-whisker plots will be provided for prespecified laboratory parameters.

For test results that will be summarized with available normal ranges, the number and percentage of subjects with the laboratory values being low (but never high), normal, high (but never low), and both low and high will be calculated for each test.

This shift summary will be produced for each test for the safety run-in/safety evaluable population as well as the subset of subjects treated at the maximum tolerated dose. The denominator for the percentage calculation will use the number of subjects in the baseline category (ie, low, high, normal, missing) as the denominator for the percentage in each of the categories during the treatment period.

For all gradable laboratory parameters, the values will be classified into grade levels corresponding to CTCAE v4.03 criteria. For specific laboratory values requiring clinical intervention to grade, the classification according to the quantitative component will be provided.

The number and percentage of subjects with the laboratory values of Grade 1, 2, 3, or 4 will be calculated for each treatment according to the largest treatment-emergent worsening of laboratory grade. Separate summaries for abnormally high and abnormally low laboratory values will be provided when the laboratory in question has both high and low grading criteria. For instance, if a subject has a baseline fasting glucose of 210 mg/dL, maximum fasting glucose after starting treatment of 245 mg/dL, and minimum fasting glucose after starting treatment of 52 mg/dL, then the subject will be counted as follows:

- The subject will be counted as a Grade 2 "Glucose decreased" in summaries of hypoglycemia because the subject was not hypoglycemic at study entry but became hypoglycemic after treatment.
- The subject will not count as a "Glucose increased" in summaries of hyperglycemia because the subject met the numeric requirements for Grade 2 hyperglycemia at baseline (fasting glucose value > 160 to 250 mg/dL) and did not increase in grade after starting treatment.

In cases where differentials of hematology parameters are obtained without corresponding absolute count data, efforts will be made to investigate if the conversion to an absolute value will lead to additional abnormalities. This will be discussed with the clinical team regarding appropriate documentation and action.

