3.1. Subject Inclusion Criteria

The following criteria are required for inclusion in the study:

1. Male or female, 18 years of age or older.
2. Histologically documented diagnosis of *de novo* DLBCL.
 - a. For Phase 1, subjects may have any DLBCL subtype.
 - b. For Phase 2, subjects must have ABC or unclassifiable subtypes of DLBCL confirmed by immunohistochemistry (IHC) using the Hans algorithm.

Subjects having a computed tomography (CT) scan abnormality with uncertain interpretation following completion of the most recent treatment regimen must have biopsy confirmation of residual DLBCL before study entry.

3. Relapsed or refractory DLBCL, defined as having received at least 1 but no more than 3 prior treatment regimens and ineligible for HDC/ASCT.
4. Fluorodeoxyglucose-avid disease (based on local evaluation) per the Lugano Classification ([Cheson et al 2014](#)). Fluorodeoxyglucose-avid disease is defined as disease with a 5-point scale (5PS) score of 4 or 5.
5. Subjects must have archived tumor tissue (block or 15-20 unstained slides) available, or be willing to undergo an incisional or excisional lymph node biopsy of accessible adenopathy (or, in less accessible lymph nodes, 4 to 8 core biopsies).
6. At least 1 measurable (≥ 2 cm in longest dimension) lesion on CT scan or magnetic resonance imaging (MRI).
7. Eastern Cooperative Oncology Group (ECOG) performance status 0 to 2.
8. Adequate bone marrow, renal, and hepatic function, per local reference laboratory ranges (values must not be achieved with growth factors) as follows:
 - a. ANC $\geq 1.5 \times 10^9/L$.
 - b. Platelet count $\geq 75 \times 10^9/L$.
 - c. Hemoglobin ≥ 8.0 g/dL (transfusions are permitted to achieve required hemoglobin level).
 - d. Serum creatinine ≤ 2.0 g/dL or measured or calculated creatinine clearance ≥ 30 mL/min by the Cockcroft-Gault Equation.

- e. Aspartate aminotransferase (AST) and ALT $\leq 2.5 \times$ institutional upper limit of normal (ULN) or $\leq 5 \times$ ULN for subjects with known hepatic metastases.
 - f. Total bilirubin $\leq 1.5 \times$ ULN if no liver metastases or $< 3 \times$ ULN in the presence of liver metastases or presence of documented Gilbert's syndrome (unconjugated hyperbilirubinemia). Further evaluation should be performed to confirm and document the origin of increase.
9. Prothrombin time (PT)/international normalized ratio (INR) $< 1.5 \times$ ULN and activated partial thromboplastin time (aPTT) $< 1.5 \times$ ULN.

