9.4.4.2. Clinical Laboratory Tests

Laboratory test values outside the normal range will be assessed for severity based on the normal ranges for the clinical reference laboratory. The incidence of abnormal laboratory values and shift tables relative to baseline will be tabulated.

Laboratory data will be classified into CTCAE grades for AEs using CTCAE v4.03. The following summaries will be produced for the laboratory data:

- Number and percentage of subjects with worst postbaseline CTCAE grade (regardless of baseline value). Each subject will be counted only for the worst grade observed postbaseline.
- Shift tables using CTCAE grades to compare baseline with the worst postbaseline value will be produced with CTCAE grade.
- For laboratory parameters where CTCAE grades are not defined, shift tables to the worst postbaseline value will be produced using the low/normal/high classifications based on laboratory reference ranges.

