10.1. Changes to Protocol-Defined Analyses

Not applicable.

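### The SAP counts laboratory grades only when they worsen from baseline, the protocol counts the worst grade regardless of baseline, and SAP 10.1 declares no change

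*SAP*

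**What the plan says.** Protocol 9.4.4.2 lists three laboratory summaries. The first is "Number and percentage of subjects with worst postbaseline CTCAE grade (regardless of baseline value"), followed by the instruction "Each subject will be counted only for the worst grade observed postbaseline". The other two are shift tables: one in CTCAE grades, and one in low/normal/high categories for tests without CTCAE grades.

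SAP 8.3.2 gives a different rule for the graded counts. The number and percentage of subjects at Grades 1, 2, 3 and 4 "will be calculated for each treatment according to the largest treatment-emergent worsening of laboratory grade". High and low abnormalities are summarized separately. The SAP then works an example: "if a subject has a baseline fasting glucose of 210 mg/dL, maximum fasting glucose after starting treatment of 245 mg/dL", with a minimum of 52 mg/dL. On the high side this subject is not counted, because the baseline value already met the Grade 2 criterion and the subject "did not increase in grade after starting treatment".

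SAP 2.1 states that the plan is based on Protocol Amendment 5, the version that contains the rule in 9.4.4.2. SAP 10.1, on changes to protocol-defined analyses, reads "Not applicable". The change log in SAP 10.2 does not mention the point.

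SAP Appendix B plans four laboratory tables: summaries of values (3.3.1.x hematology, 3.3.3.x chemistry) and shifts in CTC grade to the worst abnormal value (3.3.5.x and 3.3.6.x).

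**The concern.** The two rules can give different numbers for the same subject and test, and the SAP does not say that it has departed from the protocol. A reader of the study report who knows only the protocol would take a Grade 1 to 4 laboratory rate to include everyone who reached that grade on treatment. Under the SAP it would leave out anyone whose grade did not rise.

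The difference arises only in subjects with an abnormal grade at baseline, and the entry criteria make such subjects plausible. Protocol 3.1 accepts "Hemoglobin ≥ 8.0 g/dL (transfusions are permitted to achieve required hemoglobin level"), platelets from 75 × 10⁹/L, and AST/ALT up to 2.5 × ULN (5 × ULN with known hepatic metastases). Changes in laboratory assessments are part of the Phase 1 primary endpoint and of the Phase 2 safety endpoint, and Protocol 1.3.3 names cytopenias as an open question for the combination.

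**Working it through.** The documents state no figure to reproduce. The check compares the two rules, applies both to the SAP's example, and then looks at what the planned output would show.

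**1. The SAP's example, high side**
- Inputs (SAP 8.3.2): baseline 210 mg/dL; on-treatment maximum 245 mg/dL; Grade 2 band above 160 and up to 250 mg/dL.
- Baseline grade: 160 < 210 ≤ 250, so Grade 2. Worst postbaseline grade: 160 < 245 ≤ 250, so Grade 2.
- Protocol rule: worst postbaseline grade is 2, so the subject is counted at Grade 2 (1 of 1).
- SAP rule: the grade did not rise, so the subject is not counted (0 of 1).

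High and low are taken separately here, as the SAP does. The protocol is silent on direction.

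**2. General relation**

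For one test and one direction, let n(b, w) be the number of subjects with baseline grade b and worst postbaseline grade w.
- Protocol count at grade g = sum of n(b, g) over all b.
- SAP count at grade g = sum of n(b, g) over b < g.
- Difference = sum of n(b, g) over b ≥ g, which is zero or more.

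So the SAP count is never higher. This reads the SAP as counting a subject who worsened at the grade reached. A subject with no baseline grade enters the protocol count. The SAP does not say how such a subject is treated in its count, but excluding the subject could only lower that count further.

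**3. Size**

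The difference needs the joint distribution of baseline and worst postbaseline grade. The documents give neither, so no value for this trial can be computed.

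One limit does follow from the documents. Protocol 3.1 requires platelets of at least 75 × 10⁹/L, and Protocol 5.5.1.2 puts Grade 3 thrombocytopenia below 50 × 10⁹/L. A subject whose baseline value meets the entry limit is therefore below Grade 3, and any later Grade 3 or 4 platelet count is a worsening under both rules. The same holds for Grade 4 neutropenia: entry requires at least 1.5 × 10⁹/L, and Grade 4 is below 0.5 × 10⁹/L.

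**4. What the planned tables would show**
- Tables 3.3.5.x and 3.3.6.x set baseline grade against worst grade. Adding over the baseline rows gives the sum of n(b, g) over all b, which is the protocol count, provided all grades and missing baselines are displayed. The table shells are not in the documents.
- The only shift-table denominator SAP 8.3.2 states is the number of subjects in the baseline category, given for the low/normal/high shift. If the grade shifts follow it, the protocol's overall percentage is not printed and the reader must compute it.
- No table in Appendix B is titled as worst grade regardless of baseline, and none as treatment-emergent worsening.

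**The case against.** The strongest reply has three parts.

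- **A worsening-based count is a sound summary.** The endpoint concerns changes in laboratory assessments, and in a single-arm trial a count that ignores baseline includes abnormalities that were there before treatment. This stands. A reader might infer that the SAP rule is an error in itself. The documents do not support that; the defect is that it takes the place of the protocol's count without being declared.
- **The protocol count is probably not lost.** The shift tables use all postbaseline values, their margins should give the count, and subject-level laboratory listings (2.8.1.x to 2.8.4.x) are planned. This also largely stands, so it would be wrong to infer that the information disappears. But the protocol lists the worst-grade count and the shift tables as separate summaries, and a number a reader can reconstruct is not a number the report states.
- **Nothing decisive depends on it.** Objective response, its significance level and power are untouched. Dose-limiting toxicities follow their own criteria and investigator assessment, and adverse event tables are separate outputs. This stands in full and limits the weight of the point.

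**Conclusion.** The conflict is real: two stated rules give different counts, the SAP's example shows it, and SAP 10.1 is wrong to report no change. The direction is fixed (SAP count equal to or lower than protocol count, reading the SAP as counting at the grade reached). The size is unknown.

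A reader might infer a large understatement of laboratory toxicity. One could assume that 30% to 70% of subjects have a baseline abnormality that persists and that 30% to 70% of those worsen, which gives gaps from 0.3 × (1 − 0.7) = 9 points to 0.7 × (1 − 0.3) = 49 points. Neither share comes from the documents, so this range is not an estimate. Nor is a standard error a useful yardstick, since both counts come from the same subjects and differ by definition. Step 3 of the check also shows that Grade 3 and 4 platelet counts and Grade 4 neutrophil counts agree under both rules when the baseline value meets the entry limits.

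The consequence is confined to descriptive laboratory summaries. It should still be corrected, because a stated rule yields a different safety number from the one the protocol defines.

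**What to change.** In SAP 8.3.2 and Appendix B, add a laboratory grade table for hematology and one for chemistry, each with two separately labelled counts:
- (a) worst postbaseline CTCAE grade regardless of baseline, each subject counted once, as in Protocol 9.4.4.2;
- (b) worst grade among subjects whose grade worsened from baseline.

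Record count (b) in SAP 10.1 as an addition to the protocol-defined analysis. This does not require deciding which count is better.

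The cost is SAP wording and one new table per panel, since Appendix B has no existing table of either count to extend. All data are already collected. The raw worst-grade rates will look less favourable and will include abnormalities present before treatment, so the labels must say so.

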8.4. Vital Signs

Vital signs, including systolic blood pressure, diastolic blood pressure, pulse, respiration rate, and body temperature, will be taken with subjects in the seated position during the study in accordance with Table 8 of Protocol Amendment 5 dated 18 JUN 2020. Change and percentage change from baseline will be calculated using the last nonmissing value before first dose of study drug (Day 1) as the baseline value.

Incidences of clinically notable vital sign abnormalities are defined in [Table 5](#). The abnormal values for subjects exhibiting clinically notable vital sign abnormalities will be listed along with

their assigned treatment group. Alert vital signs are defined as an absolute value outside the defined range and percentage change > 25%.

Table 5: Criteria for Clinically Notable Vital Sign Abnormalities

Parameter	High Threshold	Low Threshold
Systolic blood pressure	> 155 mmHg	< 85 mmHg
Diastolic blood pressure	> 100 mmHg	< 40 mmHg
Pulse	> 100 bpm	< 45 bpm
Temperature	> 38°C	< 35.5°C
Respiratory rate	> 24/min	< 8/min

8.5. Electrocardiograms

Twelve-lead ECGs will be obtained for each subject during the study in accordance with Table 8 of Protocol Amendment 5 dated 18 JUN 2020. The baseline for each parameter is the average of all available values collected at screening, Day -1, and Day 1 predose. Electrocardiogram results will be reviewed for clinically notable abnormalities according to predefined criteria (see Table 6). Number and percentage of subjects with alert ECG values (outliers), defined as the absolute value outside the defined range (see Table 6) and percentage change > 25% (30% for QRS interval) will be summarized and listed if applicable. Electrocardiogram abnormalities, both at baseline and postbaseline visits, will be tabulated by treatment group. Incidences of abnormalities will be listed with study visit, assigned treatment group, and a description of the abnormality.

Table 6: Criteria for Clinically Notable Electrocardiogram Abnormalities

Parameter	High Threshold	Low Threshold
QTcF ^a	> 460 msec	< 295 msec
PR	> 220 msec	< 75 msec
QRS	> 120 msec	< 50 msec
QT	> 500 msec	< 300 msec
RR	> 1500 msec	< 600 msec

^a QTcF (Fridericia correction).

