9.4.4.3. Vital Signs

Descriptive statistics and mean change from baseline will be determined for vital signs (blood pressure, pulse, respiratory rate, and body temperature) at each assessment time. Vital sign results will be reviewed for clinically notable abnormalities (see Table 15), and subjects exhibiting clinically notable vital sign abnormalities will be listed. A value will be considered an "alert" value if it is outside of the established range and shows a > 25% change from baseline.

Table 15: Criteria for Clinically Notable Vital Signs Abnormalities

Parameter	High Threshold	Low Threshold
Systolic blood pressure	> 155 mmHg	< 85 mmHg
Diastolic blood pressure	> 100 mmHg	< 40 mmHg
Pulse	> 100 bpm	< 45 bpm
Temperature	> 38°C	< 35.5°C
Respiratory rate	> 24/min	< 8/min

[REDACTED]

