3.4.1.x	Summary of Systolic Blood Pressure	Safety Run-in / Safety Evaluable	X	X
3.4.2.x	Summary of Diastolic Blood Pressure	Safety Run-in / Safety Evaluable	X	X
3.4.3.x	Summary of Pulse	Safety Run-in / Safety Evaluable	X	X
3.4.4.x	Summary of Body Temperature	Safety Run-in / Safety Evaluable	X	X
3.4.5.x	Summary of Respiration Rate	Safety Run-in / Safety Evaluable	X	X
3.4.6.x	Summary of Body Weight	Safety Run-in / Safety Evaluable	X	X

Table No.	Title	Population ^a	Standard	In-Text
ECGs				
3.5.1.x	Summary of 12-Lead ECG: PR Interval Values	Safety Run-in / Safety Evaluable	X	X
3.5.2.x	Summary of 12-Lead ECG: QRS Interval Values	Safety Run-in / Safety Evaluable	X	X
3.5.3.x	Summary of 12-Lead ECG: QT Interval Values	Safety Run-in / Safety Evaluable	X	X
3.5.4.x	Summary of 12-Lead ECG: QTcF Interval Values	Safety Run-in / Safety Evaluable	X	X
3.5.5.x	Outliers of QT and QTcF Interval Values	Safety Run-in / Safety Evaluable	X	X
3.5.6.x	Summary of Clinically Significant ECG Abnormalities	Safety Run-in / Safety Evaluable	X	X

^a For table numbers ending in " x" the populations will be the safety run-in population for all Phase 1 tables and the ITT or safety evaluable population for Phase 2 tables.

Figures

Figure No.	Title
4.6.1	Kaplan-Meier Plot of Progression-Free Survival (Phase 2)
4.7.1	Kaplan-Meier Plot of Overall Survival (Phase 2)
4.9.1.1.1	Line Graph of Mean and STD for Hemoglobin (G/L) by Visit (Phase 1)
4.9.1.1.2	Line Graph of Mean and STD for Neutrophils (GI/L) by Visit (Phase 1)
4.9.1.1.3	Line Graph of Mean and STD for Platelets (GI/L) by Visit (Phase 1)
4.9.1.1.4	Line Graph of Mean and STD for Leukocytes (GI/L) by Visit (Phase 1)
4.9.1.2.1	Line Graph of Mean and STD for Hemoglobin (G/L) by Visit (Phase 2)
4.9.1.2.2	Line Graph of Mean and STD for Neutrophils (GI/L) by Visit (Phase 2)
4.9.1.2.3	Line Graph of Mean and STD for Platelets (GI/L) by Visit (Phase 2)
4.9.1.2.4	Line Graph of Mean and STD for Leukocytes (GI/L) by Visit (Phase 2)

Listings

Listing No.	Title
2.1.1.x	Subject Enrollment and Disposition Status
2.2.1.x	Protocol Deviations
2.3.1.x	Analysis Populations
2.3.2.x	Subject Inclusion and Exclusion Criteria
2.4.1.x	Demographics and Baseline Characteristics
2.4.2.x	Medical History
2.4.3.x	Prior Treatment Regimens
2.4.4.x	Prior Surgery
2.4.5.x	Prior Radiotherapy
2.4.6.x	Flow Cytometry
2.4.7.x	Hematopoietic Stem Cell Transplant History
2.4.8.x	DLBCL History
2.4.9.x	Prior and Concomitant Drug Treatments
2.4.10.x	PRBC/Platelet Transfusions

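### The ECG outlier rule requires an out-of-range value and a change above 25%, so the planned QTcF outlier count will miss most values above the SAP's own 460 msec limit

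*SAP*

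**What the plan says.** SAP 8.5 promises the "Number and percentage of subjects with alert ECG values (outliers" and describes these values as "defined as the absolute value outside the defined range (see Table 6) and percentage change > 25% (30% for QRS interval". Table 6 sets the QTcF range at 295 to 460 msec. The reference value is an average: "The baseline for each parameter is the average of all available values collected at screening, Day -1, and Day 1 predose".

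Appendix B of the SAP plans Table 3.5.5.x, "Outliers of QT and QTcF Interval Values". The SAP contains no other definition of an ECG outlier, no count of QTcF on the range alone, and no category for an absolute change in msec.

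Vital signs follow the same pattern. Protocol 9.4.4.3 calls a value an alert if it is "outside of the established range and shows a > 25% change from baseline". SAP 8.4 agrees: "Alert vital signs are defined as an absolute value outside the defined range and percentage change > 25" (per cent). The temperature range in SAP Table 5 is 35.5 to 38°C.

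**The concern.** One percentage condition is applied to nearly every parameter, whatever its natural variability. QTcF and body temperature move over a narrow proportional range. For them the 25% condition, not the tabulated limit, decides whether a value is flagged.

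The consequence matters most for QTcF, because there the flag feeds a reported number and percentage of subjects. Safety is the Phase 1 primary endpoint and a Phase 2 secondary endpoint, triplicate ECGs are scheduled before dosing and on Day 8, and Protocol 5.7.1 advises caution with QT-prolonging drugs. A table of outliers that is almost empty by construction could be read as evidence that QTcF prolongation did not occur.

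**Working it through.** The documents give no expected alert rate, so there is no figure of theirs to reproduce. The check applies the rule to its own limits.

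**Inputs.** Limits from SAP Tables 5 and 6; the 25% condition (30% for QRS) from SAP 8.4 and 8.5 and, for vital signs, Protocol 9.4.4.3.

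**Rule.** With baseline b, upper limit U and lower limit L, a high alert needs a value above max(U, 1.25 × b). A low alert needs a value below min(L, 0.75 × b). The upper limit is the binding condition only when b is below U/1.25.

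**QTcF.** U/1.25 = 460/1.25 = 368 msec.
- Baseline below 368: the value must exceed 460, a rise of more than 460 − 368 = 92 msec.
- Baseline of 368 or more: the rise must exceed 0.25 × b, which is at least 0.25 × 368 = 92 msec.
- So a high outlier needs a rise of more than 92 msec at any baseline.

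| Baseline (msec) | Value needed (msec) | Counted as normal although above 460 |
|---|---|---|
| 400 | > 500 | above 460, up to 500 |
| 420 | > 525 | above 460, up to 525 |
| 440 | > 550 | above 460, up to 550 |

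Example: 420 to 520 msec is a rise of 100 msec, or 100/420 = 23.8%. It lies 60 msec above the SAP's limit and is not an outlier.

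**Share of out-of-range values caught.** This step rests on assumptions that are not in the documents: normal baseline QTcF with mean 400 to 430 and SD 15 to 25 msec, and an independent normal change with mean/SD of 0/15, 10/15, 20/20 or 30/25 msec. That gives 48 scenarios, simulated with 4,000,000 draws each, counting values rather than subjects.
- Between 0.2% and 50% of values fall outside 295 to 460 msec, depending on the scenario.
- The joint rule catches 0% to 1.8% of those, and 0% to 16% of values above 500 msec.
- The scenario with the highest capture (baseline 400/15, change 30/25) has 15.15% of values out of range and 0.271% flagged: 0.271/15.15 = 1.8%.

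**Temperature.** 38/1.25 = 30.4°C, so 38°C is a rise above 25% only from a baseline below 30.4°C. Likewise 35.5/0.75 = 47.3°C, so 35.5°C is a fall above 25% only from a baseline above 47.3°C. From 37.0°C an alert needs more than 46.25°C or less than 27.75°C.

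**Where the joint rule is workable.** The upper limit still binds at ordinary baselines for several parameters: pulse below 100/1.25 = 80 bpm, systolic pressure below 155/1.25 = 124 mmHg, diastolic pressure below 100/1.25 = 80 mmHg, and QT below 500/1.25 = 400 msec.

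**The case against.** The best defence is that the plan has two tiers. Tables 5 and 6 define clinically notable values by range alone, and the alert is a stricter second label that does not replace them. Notable vital signs are listed on range alone, ECGs are reviewed against Table 6, and SAP 8.5 also has ECG abnormalities tabulated by treatment group and listed. Appendix B adds a descriptive QTcF table (3.5.4.x), a table of clinically significant abnormalities (3.5.6.x) and listings of all and of abnormal ECG values. Clinically meaningful ECG findings and clinically significant vital sign abnormalities are also reported as adverse events (Protocol 7.4.4 and 7.4.5), and the febrile neutropenia DLT uses an absolute temperature. No action and no planned table depends on the vital sign alert.

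All of that stands, and it limits the point. It does not mend the count: neither a listing nor a mean and maximum by visit gives the number and percentage of subjects with QTcF above 460 msec, and the abnormality tables are not tied to that limit.

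Two further objections have weight. Table 3.5.5.x is marked as a standard table whose shell is not in the SAP, so applying the joint rule to it is an inference, though the SAP offers no other definition. And a bare threshold would count subjects already above 460 msec before treatment, since eligibility sets no QTc limit. The fix has to deal with that.

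**Conclusion.** The point holds for the outlier count. That a high QTcF outlier needs a rise above 92 msec follows from the SAP's limits alone. That the count will miss most values above 460 msec rests on the assumed distributions, but the capture stayed at or below 1.8% across all 48 scenarios. For temperature the alert is reachable on paper but not in a patient, and the only loss is a label.

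A reader might go further and infer that QTcF prolongation or fever will go unrecorded, or that the percentage condition cancels Tables 5 and 6. The documents do not support this, because range-based review and listing and adverse event reporting do not depend on the alert. Nor do they support treating every parameter as affected: a systolic rise from 140 to above 175 mmHg (140 × 1.25) is attainable, so blood pressure is not an example of an unworkable rule.

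This should be corrected before the tables are produced. It does not touch the efficacy design.

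**What to change.** - **QTcF (SAP 8.5 and Table 3.5.5.x).** Drop the percentage condition. Count subjects with any postbaseline value outside the Table 6 range, shown separately for those within and those already outside the range at baseline. This keeps prolongation on treatment apart from prolongation present at entry. A prespecified category of absolute change in msec could be added. State the definition in a footnote to Table 3.5.5.x, because its shell is not in the SAP.
- **Temperature (SAP 8.4 and Protocol 9.4.4.3).** Define the alert by the Table 5 range alone.
- **Other parameters.** Keep the percentage condition where both conditions can plausibly be met, such as pulse and blood pressure.

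The cost is a change of wording in three sections and one programming condition. It needs no new data and alters no treatment rule. The downside is that more values will be flagged.
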